8.1.6. Summaries of Adverse Events and Deaths

A brief, high-level summary of the number and percentage of subjects who experienced at least 1 TEAE in the categories described below will be provided by treatment (by double-blind treatment for double-blind phase; by treatment sequence for extension phase):

- TEAE
- TEAEs with Grade 3 or higher (further broken down to Grade 3, Grade 4, and Grade 5)
- TEAEs with Grade 2 or higher
- TE treatment-related AE
- TE treatment-related AEs with Grade 3 or higher (further broken down to Grade 3, Grade 4, and Grade 5)
- TE treatment-related AEs with Grade 2 or higher
- TE SAE
- TE treatment-related SAE
- TEAE that led to premature discontinuation of double-blind study drug (NOTE: category applicable only for double-blind phase)

- TEAE that led to premature discontinuation of open-label filgotinib study drug (NOTE: category applicable only for extension phase)
- TEAE that led to temporary interruption of double-blind study drug (NOTE: category applicable only for double-blind phase)
- TEAE that led to temporary interruption of open-label filgotinib (NOTE: category applicable only for extension phase)
- TEAE that led to premature discontinuation of study
- All deaths observed in the study (if a subject received \geq 1 dose of open-label filgotinib or standard of care in extension phase, the death will be summarized in extension phase; if the last study drug received was double-blind drug, the death will be summarized with the double blind phase)

The number and percentage of subjects who experienced at least 1 TEAE will be provided and summarized by SOC, HLT, PT, and treatment (double-blind treatment for double-blind phase; treatment sequence for extension phase).

For other AEs described below, summaries will be provided by SOC, PT, and treatment (double-blind treatment for double-blind phase; treatment sequence for extension phase):

- All TEAEs
- All TEAEs by Concomitant Medication Use (Immunomodulator and Corticosteroid Use)
- TEAEs of Grade 3 or higher (by maximum severity)
- TEAEs of Grade 2 or higher
- All TE treatment-related AEs
- TE Treatment-related AEs of Grade 3 or higher (by maximum severity)
- TE SAEs
- TE SAEs by Concomitant Medication Use (Immunomodulator and Corticosteroid Use)
- TE treatment-related SAEs
- TEAEs leading to temporary interruption of double-blind study drug (NOTE: table applicable only for double-blind phase)
- TEAEs leading to temporary interruption of open-label filgotinib study drug (NOTE: table applicable only for extension phase)

- TEAEs leading to premature discontinuation of double-blind study drug
(NOTE: table applicable only for double-blind phase)
- TEAEs leading to premature discontinuation of open-label filgotinib study drug
(NOTE: table applicable only for extension phase)
- TEAEs leading to premature discontinuation of study
- TEAEs leading to death

Multiple events will be counted only once per subject in each summary. Adverse events will be summarized and listed first in alphabetic order of SOC and HLT within each SOC (if applicable), and then by PT in descending order of total frequency within each SOC. For summaries by severity grade, the most severe grade will be used for those AEs that occurred more than once in an individual subject during the study.

In addition to the above summary tables, all TEAEs, SAEs, and TE treatment-related AEs will be summarized by PT only and treatment (double-blind treatment for double-blind phase; treatment sequence for extension phase), in descending order of total frequency for PT.

Data listings will be provided for the following:

- All AEs, indicating whether the event is treatment emergent
- All AEs of Grade 3 or higher
- SAEs
- Deaths
- COVID-19 AEs
- All AEs leading to temporary interruption of double-blind study drug
- All AEs leading to temporary interruption of open-label filgotinib study drug
- AEs leading to premature discontinuation of double-blind study drug
- AEs leading to premature discontinuation of open-label filgotinib

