### 3.2. Extension Phase

**Figure 3-3. Extension Phase – Evaluation**

\*Open-label treatment with filgotinib or Standard of Care. Adjustment of background treatment with non-prohibited medication allowed at any time during the Extension Phase

In the Extension Phase, subjects will receive open-label treatment (filgotinib or Standard of Care) and have a study visit every 13 weeks that includes semen analysis. The first scheduled visit of the Extension Phase occurs at Week 26.

In case sperm parameters at any visit (including Week 156) meet any of the pre-specified decrease thresholds, subjects will enter the Monitoring Phase.

During the Extension phase, Standard of Care and background treatment concomitant to filgotinib may be optimized at the discretion of the investigator, taking into consideration the protocol restrictions.

[figure not shown]
In case a subject needs to be treated with a prohibited medication (see [Table 5-1](#)), for instance to control their rheumatic condition, the subject will discontinue the study and complete an Early Termination (ET) visit (including semen collection). For subjects on filgotinib, this will be followed by a safety follow-up visit 30 days after last study drug dose.

All subjects who did not enter the Monitoring Phase will continue the study until the Week 156 visit.

In the Extension Phase, subjects must have yearly Quantiferon® testing. Yearly TB testing begins 1 year from the screening TB test date. If yearly TB testing falls between study visits, the yearly TB testing should be performed at the visit prior to 1 year from the screening TB test date. Subjects with newly positive (converted) Quantiferon® (or centrally reported equivalent assay) TB test should be discontinued from the study. Subjects who were previously treated for TB with a complete and adequate course of therapy as per local Standard of Care and as verified by the investigator do not need to have yearly tests.

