**Table 5-1. Prohibited Concomitant Medications**

Drug Class	Agents Disallowed	Prohibited Period
Strong P-gp Inducersa		
Anticonvulsants	Including, but not limited to Phenobarbital, phenytoin, carbamazepine	21 days prior to Screening through the end of the Double-blind Treatment Phase of the study and through the end of the Extension Phase for subjects on open-label filgotinib
Antimycobacterials	Including, but not limited to Rifabutin, rifapentine, rifampin	
Herbal/Natural Supplements	St. John's wort and danshen ( Salvia Miltiorrhiza )	
Prohibited Medications for Rheumatic Conditions		
Corticosteroids	Dose equivalent to >10 mg/day of prednisone or equivalent (oral) For subjects on Standard of Care treatment: dose equivalent to >20 mg/day of prednisone or equivalent (oral) All parenteral corticosteroids are prohibited During the Extension and Monitoring Phase, subjects may receive a maximum of 3 intra-articular injections of corticosteroid every 12 months; The dose of corticosteroid injected should not exceed the equivalent dose of triamcinolone 40-mg suspension; The dose and volume should be adjusted downward as appropriate to the size of the joint	Randomization through the end of the study
TNF $\alpha$ antagonist	Including, but not limited to: infliximab, adalimumab, etanercept, golimumab, certolizumab, and biosimilar agents	4 weeks prior to Screening through the end of the Double-Blind Treatment Phase of the study and through the end of the Extension Phase for subjects on open-label filgotinib
Interleukin antagonists	Including, but not limited to: ustekinumab, toccilizumab, secukinumab, anakinra,	12 weeks prior to Screening through the end of the Double-Blind Treatment Phase of the study and through the end of the Extension Phase for subjects on open-label filgotinib
JAK inhibitor	Any JAK inhibitor other than filgotinib	90 days prior to Screening through the end of the Double-Blind Treatment Phase of the study and through the end of the Extension Phase for subjects on open-label filgotinib

Drug Class	Agents Disallowed	Prohibited Period
	Filgotinib	Any time prior to Randomization in this study

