- Subjects with a decrease of $\geq 50\%$ in sperm concentration and/or motility and/or morphology from baseline while on double-blind treatment or open-label filgotinib will have study drug stopped and an investigator selected standard of care treatment that meets protocol-specified criteria started. Subjects meeting a sperm decrease while on standard of care in extension phase will continue on a standard of care regimen. Semen samples will be collected off-study drug/control (eg, standard of care in extension phase) every 13 weeks during the Monitoring Phase until reversibility is met or for up to 52 weeks, whichever occurs first. Reversibility is met when all sperm parameter(s) qualifying the subject to enter the Monitoring Phase return to greater than 50% of the baseline value (ie, greater than $0.5 \times$ [mean of 2 evaluable samples collected at the screening visit]). Data will be summarized for each sperm parameter meeting a pre-specified sperm decrease threshold at the visit when study drug was stopped. The number (percent) who met reversibility criteria and the cumulative number (percent) who met reversibility criteria at each Monitoring Phase visit will be presented separately for subjects who met pre-specified sperm parameter decreases at Week 13 (summarized by double-blind treatment group); for subjects meeting pre-specified sperm parameter decrease thresholds at Week 26 (summarized by treatment sequence and rheumatic disease responder/ non-responder status at Week 13) and at or after Week 39 (summarized by treatment sequence).

For the safety analyses, subjects will be grouped by double-blind treatment group (ie, filgotinib 200 mg or placebo) for safety events reported during the double-blind phase of the study.

Safety events reported during the extension phase will be summarized by treatment sequence (double-blind filgotinib to open-label filgotinib, double-blind filgotinib to standard of care, and placebo to standard of care).

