3.7. Analysis Visit Windows

3.7.1. Definition of Study Day

The First Dosing Date of Double-Blind Filgotinib/Placebo is defined as the date when subjects take their first dose of double-blind filgotinib/placebo as recorded on the Study Drug Administration eCRF.

The Last Dosing Date of Double-Blind Filgotinib/Placebo is defined as the date when subjects take their last dose of double-blind filgotinib/placebo as recorded in the Study Drug Administration eCRF.

The Last Dosing Date of Any Filgotinib is defined as the date when a subject takes their last dose of double-blind or open-label filgotinib as recorded in the Study Drug Administration eCRF.

The Start Date of Extension Phase is defined as the first dose date of open-label filgotinib (for rheumatic disease responders randomized to filgotinib who continued on open-label filgotinib in extension phase) from the study drug administration eCRF or last dose date of double-blind study drug +1 day for subjects who have a non-missing standard of care start date in the extension phase of the study. In some countries, it takes time to obtain a new standard of care drug for rheumatic disease when subjects undergo a medication switch (especially for biologics), so the “standard of care” is to continue background medications alone or in rare cases, to take no rheumatic disease medication until the new regimen is available.

The End Date of Extension Phase is defined as last dose date of open-label filgotinib as recorded on the Study Drug Administration eCRF for subjects on open-label filgotinib in the Extension Phase. The end date for standard of care in extension phase will be 1 day prior to the date the subject went into the Monitoring Phase (ie, date the site was notified of subject meeting a prespecified sperm decrease threshold). Subjects who do not participate in Monitoring Phase but have a Study Completion eCRF that states that the subject has either completed study or prematurely discontinued study will have the last date of standard of care estimated using the last of the following dates: last Covance lab date, last eCRF visit date, date of last sperm sample collection, and death date (if subject died).

Study Day will be calculated from the first dosing date of double-blind filgotinib/placebo and derived as follows:

- For postdose study days: Assessment Date – On-Filgotinib/Placebo Study Day 1 + 1
- For days prior to the first dose: Assessment Date – On-Filgotinib/Placebo Study Day 1

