6.5.3. Pre-Specified Sperm Decrease Threshold Criteria and Confirmed Semen Abnormalities

Subjects who met a pre-specified sperm decrease threshold (a $\geq 50\%$ decrease from baseline in sperm concentration and/or motility and/or morphology) were to stop study drug and begin a standard of care regimen selected by the investigator in accordance with the protocol and be followed off study drug to evaluate for reversibility criteria.

A “confirmed semen abnormality” as defined by Jarvi and colleagues {[Jarvi 2008](#)} reflects the presence of abnormal sperm parameters potentially associated with decreased male fertility; the criterion is met when one or more of the following are observed: a sperm concentration $< 5 \text{ M/mL}$, or sperm motility $< 20\%$, or a percent normal sperm morphology of $< 10\%$.

The number and proportion of subjects meeting any of the sperm decrease thresholds (from the baseline value [mean of 2 evaluable semen collections at screening]) or any of the components of a confirmed semen abnormality (mean of 2 evaluable samples at a study visit) at Week 13 will be displayed by double-blind treatment group for the Semen Analysis Set.

Sperm Decrease Criteria

- $\geq 50\%$ decrease in sperm concentration
- $\geq 50\%$ decrease in sperm total motility
- $\geq 50\%$ decrease in sperm morphology [% normal] (WHO 1992 criteria)
- $\geq 50\%$ decrease in sperm concentration and ($\geq 50\%$ decrease in total motility and/or morphology [% normal]) at the same visit)

Confirmed Semen Abnormality Criteria (as defined by Jarvi et al)

- Sperm concentration $< 5 \text{ M/mL}$
- Sperm total motility $< 20\%$
- Sperm morphology (% normal) $< 10\%$
- Confirmed Semen Abnormality (Sperm concentration $< 5 \text{ M/mL}$ or sperm total motility $< 20\%$ or sperm morphology [% normal] $< 10\%$ at the same visit)

The number and proportion of subjects meeting any of the pre-specified sperm decrease thresholds or components of a confirmed semen abnormality will be displayed at Week 26 for the Week 26 Semen Analysis Set; and at or after the Week 39 visit for the At/After Week 39 Semen Analysis Set. Presentations will be displayed by treatment sequence and responder/non-responder at Week 13 and treatment sequence, respectively.

A listing of subjects who met any of the components of a confirmed semen abnormality will be provided.

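### Extension-phase harms are shown by treatment sequence only as crude percentages, although time at risk can differ between sequences and so mislead in either direction

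*SAP*

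**What the plan says.** - **Measure.** SAP 3.2: "Safety events reported during the extension phase will be summarized by treatment sequence". There are three sequences: filgotinib to open-label filgotinib, filgotinib to Standard of Care, and placebo to Standard of Care. SAP 8.1.6 gives n (%) for any TEAE, Grade 2 or higher, Grade 3 or higher, related events, SAEs and others. These tables "will be provided by treatment (by double-blind treatment for double-blind phase; by treatment sequence for extension phase".
- **End of the clock (SAP 3.7.1).** On open-label filgotinib: "The End Date of Extension Phase is defined as last dose date of open-label filgotinib". On Standard of Care it is the day before Monitoring Phase entry. Subjects who never enter that phase and have completed or left the study "will have the last date of standard of care estimated using the last of the following dates": laboratory, visit, sperm sample or death.
- **The 30-day tail.** SAP 8 adds 30 days for both treatments. The first extension criterion in SAP 8.1.5.1 states an end only for open-label filgotinib, but the worked example below it gives Standard of Care 30 days too. An event that leads to stopping open-label filgotinib counts under its own criterion, with no date limit.
- **Exit rules.** In Protocol Table 5-1 the bar on TNF antagonists, interleukin antagonists, other JAK inhibitors and other non-biologic DMARDs runs past the double-blind phase "through the end of the Extension Phase for subjects on open-label filgotinib". If a prohibited drug is needed (Protocol 3.2), "the subject will discontinue the study and complete an Early Termination (ET) visit".
- **Exposure-adjusted rates (SAP 8.1.5.3 and 8.1.7).** These are planned for SAEs and adverse events of interest, for the double-blind phase and for the overall study (filgotinib and placebo). A rate difference is planned only for the double-blind phase.
- **Sperm.** SAP 6.5.3 shows the share meeting a decrease threshold at Week 26 "and at or after the Week 39 visit for the At/After Week 39 Semen Analysis Set". SAP 6.5.2 gives proportions by visit for sperm concentration only.

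**The concern.** A crude percentage is a fair summary of harm only if the groups are watched for similar lengths of time. Here the filgotinib window closes when the drug stops. The Standard of Care window stays open when a drug is stopped or switched, because it closes on leaving the phase or on last contact. A subject on open-label filgotinib who needs one of the four drug classes above must leave the study, while a subject on Standard of Care may take it and stay. Someone who leaves at Week 40 still counts as a whole subject in the denominator.

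The extension lasts up to 143 weeks and is the long-term safety evidence in this trial. Readers will set the sequence columns side by side even though no test is planned. If average time at risk differs, a gap between columns may reflect follow-up rather than drug, and equal columns may hide a real gap.

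**Working it through.** **Plan's own figure.** Extension length: 156 − 13 = 143 weeks = 1001 days = 2.741 years, as Protocol 3.6 states. The tail is 30 days = 0.082 years, and 30/1001 = 3.0% of the maximum.

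**Inputs not in the documents (assumed).** A constant event rate λ, the same in both groups, of 0.05, 0.20 or 1.0 per year, and a constant exit rate μ from the window of 0.1, 0.3 or 0.5 per year.

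**Formula.** With T = 2.741, g = 0.082 and k = λ + μ:

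crude risk = 1 − e^(−λg) × [ (μ/k)(1 − e^(−kT)) + e^(−kT) ]

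Example, λ = 0.20 and μ = 0.3: e^(−0.5×2.741) = 0.254. The bracket is 0.6 × 0.746 + 0.254 = 0.702. Times e^(−0.0164) = 0.984 this gives 0.690, so crude risk = 31.0%.

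**Results at λ = 0.20, filgotinib / Standard of Care.**

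| Exit rate per year | Mean window, years | Crude % | Ratio |
|---|---|---|---|
| 0.3 / 0.3 | 1.95 / 1.95 | 31.0 / 31.0 | 1.00 |
| 0.3 / 0.1 | 1.95 / 2.48 | 31.0 / 38.4 | 0.81 |
| 0.5 / 0.1 | 1.57 / 2.48 | 25.6 / 38.4 | 0.67 |
| 0.1 / 0.3 | 2.48 / 1.95 | 38.4 / 31.0 | 1.24 |
| 0.1 / 0.5 | 2.48 / 1.57 | 38.4 / 25.6 | 1.50 |

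The ratio runs from 0.64 to 1.56 at λ = 0.05 and from 0.78 to 1.28 at λ = 1.0. With events and person-time cut at the same date, the exposure-adjusted rate is 20.0 per 100 patient-years in every row.

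**What drives it.** Dropping the 30-day tail changes a crude risk by a factor of only 1.01 to 1.05. Unequal time at risk is what matters.

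**Can SAP 8.1.5.3 be reused as it stands?** No.
- It starts person-time at the double-blind phase.
- It ends filgotinib-to-Standard-of-Care subjects at the last double-blind dose, so they have no extension time.
- It gives placebo-to-Standard-of-Care subjects no extra 30 days, although SAP 8 counts their events that far. Under the assumptions above, that mismatch overstates their rate by about 1% to 5%.

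**Sperm display.** Weeks 39 to 156 hold (156 − 39)/13 + 1 = 10 visits. If SAP 6.5.3 is read as an ever-met count, an assumed 3% chance per visit gives 1 − 0.97^10 = 26.3% with full follow-up. If 25% or 40% of subjects leave evenly over visits 1 to 10, it gives 23.5% or 21.8%.

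**The case against.** A reader might infer that harms are under-counted on filgotinib. The documents do not support that.

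- Both treatments carry the 30-day tail, and Standard of Care time stops at Monitoring Phase entry. Its window is therefore not all time in study.
- A sperm decrease closes either window. Several drugs in Table 5-1, such as sulfasalazine and rituximab, are barred for everyone to the end of the study.
- Only Week 13 responders continue on filgotinib, while non-responders without a sperm decrease go to Standard of Care. Filgotinib subjects could well stay longer.
- A subject who leaves the study for a prohibited drug has little data beyond the 30-day visit to lose. The documents do not clearly say whether someone who stops filgotinib for another reason stays in follow-up. Only then would later events be collected and left out.
- A one-sided illustration is easy to build. At 20 per 100 patient-years, full follow-up gives 43.1%, against 38.4% or 35.6% if 25% or 40% of filgotinib subjects stop evenly over the extension, a gap of 4.7 to 7.5 points. It assumes that nobody leaves Standard of Care in 143 weeks.

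It can also be said that much is already planned: overall-study rates for SAEs and adverse events of interest, weeks on open-label filgotinib or in the extension (SAP 4.2.1), and by-visit sperm concentration. The displays are descriptive, and the sequences are formed by response rather than randomisation.

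All of this stands, and it removes any claim about direction. It does not supply a rate by sequence, or any rate for any TEAE or Grade 3 or higher. The overall-study display also mixes double-blind and extension time.

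**Conclusion.** The point holds as one of measurement. Extension-phase percentages by sequence rest on windows that end on different events and on exit rules that differ by sequence, so time at risk can differ and the percentages can mislead either way. A shorter filgotinib window is plausible from Table 5-1 but is not shown.

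The possible size is a crude ratio of 0.64 to 1.56 when the true rates are equal. That range rests wholly on assumed constant event and exit rates. If exit rates match, there is no distortion. Exposure adjustment removes the effect of unequal time only. It does not remove selection by Week 13 response or exit related to prognosis, and it is less clean if event rates change over time.

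This is worth changing, but it does not touch the primary endpoint or the double-blind safety comparison.

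**What to change.** 1. In SAP 8.1.6, add extension-phase exposure-adjusted incidence rates with exact 95% CIs by treatment sequence for any TEAE, Grade 3 or higher, SAE and each adverse event of interest. Show weeks at risk beside the crude percentages.
2. In SAP 8.1.5.3, add extension-phase dates. Person-time starts at the extension start date of SAP 3.7.1. One identical end rule, extension end date plus 30 days (or death or data cutoff if earlier), applies to every sequence and to both events and person-time.
3. In SAP 8.1.5.1, state the Standard of Care end date in the criterion itself. Reconcile the worked example, which describes a placebo subject but labels the events as filgotinib.
4. Label the displays descriptive and non-randomised, and add no test between sequences.
5. Secondary: in SAP 6.5.3, add a rate per patient-year or a cumulative incidence by sequence for sperm decreases at or after Week 39, since motility and morphology have no by-visit proportions.

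The cost is a few extra tables and new date definitions, with no new data. Intervals for rare events of interest will be wide. The SAP is already final, so the addition would be recorded in the clinical study report, as SAP 1 requires for later changes.
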